7.7.2. Key Secondary Endpoints

The key secondary efficacy endpoints are CR, OS, CR+CRh, and OR. CR, CR+CRh and OR will be assessed until the date of relapse (that is subsequently confirmed). Only assessments performed on or before the start date of subsequent anticancer therapies will be considered in the determination of these response endpoints.

7.7.2.1. Complete Remission

Complete remission rate is defined as the proportion of subjects who achieve a CR. If the primary analysis of EFS is significant, a CMH test stratified by the randomization stratification factors will be used to compare CR rate between the 2 treatment arms at 1-sided 2.5% level of significance. The odds ratio and its associated 95% CI will be presented.

7.7.2.2. Overall Survival

Overall survival is defined as the time from date of randomization to the date of death due to any cause. If a subject is not known to have died by the data cutoff date, then OS will be censored at the date of last contact (see [Section 6.3.7](#)).

If the primary analyses of EFS and CR rate are significant, OS will be tested using the log-rank test stratified by the randomization stratification factors at 1-sided 2.5% level of significance.

The HR will be estimated using a Cox's PH model stratified by the randomization strata. Each stratum will define a separate baseline hazard function (using the "STRATA" statement in SAS PROC PHREG), ie for the i -th stratum the hazard function is expressed as: $h(i;t)=h(i,0;t)\exp(x\beta)$, where $h(i,0;t)$ defines the baseline hazard function for the i -th stratum

and x defines the treatment arm (0=control arm, 1=treatment arm) and β is the unknown regression parameter. Ties will be handled by replacing the PH model by the discrete logistic model (Ties=Discrete option in SAS PROC PHREG).

Kaplan-Meier estimates (product-limit estimates) will be presented by treatment arm together with a summary of associated statistics including the median OS time with 2-sided 95% CIs. In particular, the OS rate at 3, 6, 9, 12, 18, 24 and 36 months will be estimated with corresponding 2-sided 95% CIs. The CIs for the median will be calculated according to Brookmeyer and Crowley and the CIs for the survival function estimates at the time points defined above will be derived using the log-log transformation (confotype=loglog default option in SAS PROC LIFETEST) with back transformation to a CI on the untransformed scale. The estimate of the SE will be computed using Greenwood's formula.

Frequency of subjects with an event (death) and censoring reasons will be presented by treatment arm. Reasons for censoring will be summarized according to the categories in Table 7 following the hierarchy shown.

Table 7: OS Censoring Reasons and Hierarchy

Hierarchy	Condition	Censoring Reason
1	No event and (EOS date \geq date of randomization when reason for EOS=Withdrawal by Subject)	Withdrawal of consent
2	No event and [(lost to follow-up in any disposition page or survival follow-up page) or (data cutoff date–last contact date >8 weeks)]	Lost to follow-up
3	No event and none of the conditions in the prior hierarchy are met	Alive

Abbreviations: OS=overall survival; EOS=end of study.

The OS event or censoring time and the reasons for censoring will also be presented in a by-subject listing.

7.7.2.3. Complete Remission Plus Complete Remission with Partial Hematologic Recovery

The CR+CRh rate is defined as the proportion of subjects who achieved a CR or CRh. CRh is defined as a CR with partial recovery of peripheral blood counts [$<5\%$ bone marrow blasts, ANC $>0.5 \times 10^9/L$ (500/ μ L), and platelets $>50 \times 10^9/L$ (50,000/ μ L)].

Since CRh is not part of modified IWG criteria, it will be derived by the Sponsor based on the following rules, for each individual assessment which is not CR.

- Bone marrow blast $<5\%$, and
- Closest ANC within ± 8 days $>0.5 \times 10^9/L$, and
- Closest platelet counts within ± 8 days $>50 \times 10^9/L$, and
- Assume negative if Auer rod is not reported, and
- Assume negative if extramedullary disease is not reported

For bone marrow blasts, bone marrow aspirate will be used as the primary source. If a bone marrow aspirate assessment is not available, a bone marrow biopsy assessment will be used.

For ANC or platelet count, if there are 2 values which have the same distance to the bone marrow assessment date (eg, one is 1 day prior and the other is 1 day after), the value from the earlier assessment date will be used.

If the primary analyses of EFS, CR and OS are statistically significant, a CMH test stratified by the randomization stratification factors will be used to compare the CR+CRh rate between the 2 treatment arms at 1-sided 2.5% level of significance. The odds ratio and its associated 95% CI will be presented.

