Complete remission rate is defined as the proportion of subjects who achieve a CR. A Cochran Mantel-Haenszel (CMH) test will be used to compare CR rate between the 2 treatment arms. A logistic regression model will be used to estimate the treatment effect in terms of an odds ratio. The odds ratio and its associated 95% CIs will be presented.

Overall survival is defined as the time from date of randomization to the date of death due to any cause. Kaplan-Meier curves and KM estimates of OS will be presented for each treatment arm, including estimates of the median and other quantiles, as well as individual time points (eg, 3-, 6-, and 12-month rates). The log-rank test stratified by the randomization factors will be used to compare OS between the 2 treatment arms. The HR of OS with a 95% CI comparing the AG-120 + azacitidine arm with the placebo + azacitidine arm will be estimated from a Cox proportional hazards model stratified by the randomization stratification factors.

The CR + CRh rate is defined as the proportion of subjects who achieved a CR or CRh. CRh is defined as having all CR criteria except that ANC is $>0.5 \times 10^9/L$ ($500/\mu L$) and platelet count is $>50 \times 10^9/L$ ($50,000/\mu L$). Because CRh is not part of modified IWG response criteria, it will be derived by Sponsor. A CMH test will be used to compare the CR + CRh rate between the 2 treatment arms. A logistic regression model will be used to estimate the treatment effect in terms of an odds ratio. The odds ratio and its associated 95% CIs will be presented.

Objective response rate is defined as the rate of CR, CRi (including CRp), PR, and MLFS. The best response is calculated using the following hierarchy: 1) CR; 2) CRi (including CRp); 3) PR; and 4) MLFS. A summary of best response by treatment arm will be produced. A CMH test will be used to compare ORR between the 2 treatment arms. A logistic regression model will be used to estimate the treatment effect in terms of an odds ratio. The odds ratio and its associated 95% CIs will be presented.

Additional Secondary Endpoint Analyses:

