8.2. Inclusion Criteria

Subjects must meet all of the following criteria to be eligible for inclusion in the study:

1. Be ≥ 18 years of age and meet at least 1 of the following criteria defining ineligibility for intensive IC:
 - a. ≥ 75 years old
 - b. ECOG PS = 2
 - c. Severe cardiac disorder (eg, congestive heart failure requiring treatment, LVEF $\leq 50\%$, or chronic stable angina)
 - d. Severe pulmonary disorder (eg, diffusing capacity of the lungs for carbon monoxide $\leq 65\%$ or forced expiratory volume in 1 second $\leq 65\%$)
 - e. Creatinine clearance < 45 mL/minute
 - f. Bilirubin > 1.5 times the upper limit of normal (\times ULN)
 - g. Any other comorbidity that the Investigator judges to be incompatible with intensive IC must be reviewed and approved by the Medical Monitor before study enrollment.
2. Have previously untreated AML, defined according to WHO criteria. Subjects with extramedullary disease alone (ie, no detectable bone marrow and no detectable peripheral blood AML) are not eligible for the study.
3. Have an IDH1 mutation resulting in an R132C, R132G, R132H, R132L, or R132S substitution, as determined by central laboratory testing (using an investigational polymerase chain reaction [PCR] assay, Abbott RealTime IDH1) in their bone marrow aspirate (or peripheral blood sample if bone marrow aspirate is not available, with Medical Monitor approval).

(Note: Local testing for eligibility and randomization is permitted with Medical Monitor approval; however, results must state an IDH1 mutation resulting in an R132C, R132G, R132H, R132L, or R132S substitution. Bone marrow aspirate [or peripheral blood sample if bone marrow aspirate is not available, with Medical Monitor approval] for central laboratory testing must have been sent with proof of shipment to the central laboratory prior to randomization.)
4. Have an ECOG PS score of 0 to 2.
5. Have adequate hepatic function, as evidenced by:
 - a. Serum total bilirubin $\leq 2 \times$ ULN, unless considered to be due to Gilbert's disease or underlying leukemia, where it must be $< 3 \times$ ULN.
 - b. Aspartate aminotransferase (AST), alanine aminotransferase (ALT), and alkaline phosphatase (ALP) $\leq 3.0 \times$ ULN, unless considered to be due to underlying leukemia.

6. Have adequate renal function, as evidenced by serum creatinine $\leq 2.0 \times$ ULN or creatinine clearance > 30 mL/min based on the Cockcroft-Gault glomerular filtration rate.

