Table 10: Modified International Working Group Response Criteria for Acute Myeloid Leukemia

Category	Definition
Complete remission (CR) ^a	Bone marrow blasts <5% and no Auer rods; absence of extramedullary disease; ANC $\geq 1.0 \times 10^9/L$ (1000/ μ L); platelet count $\geq 100 \times 10^9/L$ (100,000/ μ L); independence of red blood cell transfusions
CR with incomplete recovery (CRi), including CR with incomplete platelet recovery (CRp) ^b	All CR criteria except for residual neutropenia (ANC < $1.0 \times 10^9/L$ [1000/ μ L]) or thrombocytopenia (platelet counts < $100 \times 10^9/L$ [100,000/ μ L]; without platelet transfusion for at least 1 week prior to disease assessment)
Morphologic leukemia-free state (MLFS)	Bone marrow blasts <5% and no Auer rods; absence of extramedullary disease; no hematologic recovery required
Partial remission (PR)	All hematologic criteria of CR; decrease of bone marrow blast percentage to 5%-25%; and decrease of pretreatment bone marrow blast percentage by at least 50%
Relapse (defined only for subjects who have previously attained CR, CRi, CRp, or MLFS) ^c	Bone marrow blasts $\geq 5\%$; or reappearance of blasts in the blood; or development of extramedullary disease

Source: (Cheson et al. 2003; Döhner et al. 2017; Sievers et al. 2001).

Abbreviations: AML = acute myeloid leukemia; ANC = absolute neutrophil count; IWG = International Working Group; MDS = myelodysplastic syndrome.

Note: Modified to remove molecular complete remission (CRm) and cytogenetic complete remission (CRc).

^a All criteria need to be fulfilled; marrow evaluation should be based on a count of 200 nucleated cells in an aspirate with spicules; if ambiguous, consider repeat exam after 5 to 7 days; flow cytometric evaluation may help to distinguish between persistent leukemia and regenerating normal marrow; a marrow biopsy should be performed in cases of dry tap, or if no

spicules are obtained; no minimum duration of response required. ANC $\geq 1.0 \times 10^9/L$ (1000/ μL) per the European LeukemiaNet guidelines.

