12.11. Procedures for Handling Missing, Unused, and Spurious Data

No imputation will be performed for missing data elements unless specified otherwise.

When tabulating AE data, partial dates will be imputed. Rules of imputation will be specified in the SAP. All response assessments occurring after documented confirmed relapse/progression maybe be listed and analyzed separately.

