7.3.2. Disease Characteristics

The following baseline characteristics of the underlying disease will be summarized based on the data entered in the eCRF:

- Disease type
 - Nature of AML per Investigator [de novo; secondary (treatment-related AML; history of MDS; history of MPD; other)]
 - WHO classification of AML (AML with genetic abnormalities; AML with myelodysplasia-related changes; therapy-related myeloid neoplasms; AML not otherwise specified)
- ECOG PS at baseline (0; 1; 2; 3; 4)
- IDH1 mutation type at baseline based on central testing (R132C; R132G; R132H; R132L; R132S; wild type). Results from bone marrow will be used as the primary source. If results from bone marrow are not available, the results from peripheral blood will be used instead.
- IDH1 mutation status at baseline based on local testing (positive; negative)
- Cytogenetic results (normal karyotype; abnormal karyotype) and cytogenetic risk status according to the Investigator based on NCI NCCN guidelines (favorable; intermediate; poor; other)
- Baseline bone marrow aspirate blasts (%)
- Baseline bone marrow biopsy blasts (%)
- Baseline peripheral blood blasts (%)
- Baseline values of the following laboratory parameters. These parameters will be summarized as continuous variables as well as categorical variables using the specified category:
 - WBC (<15×10⁹/L; 15 to <30×10⁹/L; ≥30×10⁹/L)
 - ANC (<0.5×10⁹/L; 0.5 to <1×10⁹/L; ≥1.0×10⁹/L)
 - Hemoglobin (<80 g/L; ≥80 g/L)

- Platelet count ($<50 \times 10^9/L$; 50 to $<100 \times 10^9/L$; $\geq 100 \times 10^9/L$)
- Lactate dehydrogenase (LDH)
- Creatinine clearance (<15 mL/min; 15 to <40 mL/min; 40 to <60 mL/min; 60 to <90 mL/min; ≥ 90 mL/min)
- Extramedullary disease at baseline (yes; no; unknown; not assessed)

Data on disease characteristics will be provided in by-subject listings.

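### The CRh derivation treats unreported extramedullary disease and Auer rods as absent even after a documented positive, so a few assessments called neither CR, CRi nor MLFS could be counted as CRh

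*SAP*

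**What the plan says.** - **Definition.** The Protocol Synopsis (key secondary endpoint analyses) states that "CRh is defined as having all CR criteria except that ANC is" above 0.5 × 10⁹/L and platelets are above 50 × 10⁹/L. Protocol Table 10 (Section 10.8.1) includes among the CR criteria "Bone marrow blasts <5% and no Auer rods; absence of extramedullary disease". Both absences therefore carry over to CRh.
- **Derivation.** SAP 7.7.2.3 has the Sponsor derive CRh "for each individual assessment which is not CR". It needs marrow blasts <5%, and the closest ANC and platelet count within ±8 days above the two limits. It then adds "Assume negative if Auer rod is not reported" and "Assume negative if extramedullary disease is not reported".
- **Who can be enrolled.** Protocol 8.2, Inclusion Criterion 2: "Subjects with extramedullary disease alone (ie, no detectable bone marrow and no detectable peripheral blood AML) are not eligible for the study". Extramedullary disease alongside marrow or blood disease is allowed.
- **What is recorded at baseline.** SAP 7.3.2 lists "Extramedullary disease at baseline (yes; no; unknown; not assessed" as a baseline characteristic. It lists no baseline field for Auer rods.
- **Role of the endpoint.** CR+CRh is fourth in the fixed sequence (EFS, CR, OS, CR+CRh, OR), tested by a stratified CMH test at 1-sided 2.5% (SAP 6.2.1 and 7.7.2.3).

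Neither document carries a known positive forward, asks for an explicit negative after one, or plans a sensitivity analysis of the two defaults.

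**The concern.** Reading a blank as negative is reasonable for a feature the subject never had. It is not reasonable for one already documented. Under the SAP wording, a subject with recorded baseline extramedullary disease and a blank field after baseline is treated as free of it, and can become CRh on marrow and counts alone.

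Blanks are foreseeable. Protocol 10.8.1 assesses response from marrow, blood counts and blood films, and no extramedullary imaging is scheduled. Examinations on Day 1 of each cycle are limited and symptom-directed, although a skin examination is mandatory (Protocol 10.6.2).

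At stake is the CR+CRh rate, which is alpha-controlled, together with TTCRh and DOCRh, which take their dates from the first CR or CRh. DOCRh has a further problem. Relapse is defined only after CR, CRi, CRp or MLFS (Protocol Table 10), and progression is an event only for DOR (SAP Table 8, footnote). A subject derived as CRh but held at stable disease by the investigator could later progress without a DOCRh event.

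**Working it through.** **1. The plan's own figure.** Inputs from SAP Table 4: 45% vs 25%, 200 subjects, 1:1, 1-sided 2.5%; stated power 84%. Pooled-variance normal approximation with 100 per arm:

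- SE under the null = √(0.35 × 0.65 × 2/100) = 0.0675
- SE under the alternative = √(0.25 × 0.75/100 + 0.45 × 0.55/100) = 0.0660
- Power = Φ[(0.20 − 1.96 × 0.0675)/0.0660] = Φ(1.03) = 84.8%

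This agrees with the stated 84%.

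**2. Where the default can change a result.** Investigator calls other than CR, under Protocol Tables 10 and 11:

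| Investigator call | Can it reach CRh through the default alone? |
|---|---|
| CRi (including CRp) | No. All CR criteria except counts are met, so both absences are already judged. |
| MLFS | No. Blasts <5%, no Auer rods and no extramedullary disease are required; no count recovery is needed. |
| PR | No. Blasts are 5-25%. |
| Stable disease or not evaluable, with blasts <5% and qualifying counts | Yes. |

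In the last row, an evaluable assessment with blasts <5% that is not even MLFS can fail only on Auer rods or extramedullary disease, unless the call is an error. Those are the two items that the default resolves in favour of response. A true CRh always satisfies MLFS. A CRh created this way could therefore count towards CR+CRh without counting towards ORR, which uses CR, CRi, PR and MLFS (SAP 7.7.2.4).

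The CR+CRh rate changes only if the subject has no CR and no valid CRh at another assessment. Otherwise only the TTCRh and DOCRh dates can move.

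**3. How many subjects.** The documents give neither the prevalence of baseline extramedullary disease nor the frequency of blank fields. Assumption: 2-10% have it at baseline.

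- Exposed: 200 × 0.02 = 4, to 200 × 0.10 = 20
- Planned CRh increment over CR (SAP 6.2.1): 25% − 20% = 5 points, and 45% − 40% = 5 points
- Expected: 4 × 0.05 = 0.2, to 20 × 0.05 = 1 subject

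This is before requiring that the field be blank and the call be neither CRi nor MLFS, both of which lower it. One subject in an arm of 100 is 1 percentage point, against a planned CRh contribution of 5 points.

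**4. What one point does (illustration only).** Same formula as step 1:

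| Scenario | Result |
|---|---|
| 1 point removed from both arms (44% vs 24%) | power 85.3% |
| 1 point removed from the AG-120 arm only (44% vs 25%) | power 81.2% |
| True rate 25% in both arms, 1 false point in the AG-120 arm only | rejection rate about 3.6% instead of 2.5% |

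**The case against.** The strongest defence is that the safeguard already exists. Most assessments with blasts <5% and incomplete counts should be investigator CRi or MLFS, and both calls affirm that the two features are absent. There the default only fills a blank in line with that judgement. This stands, and it limits the point to the last row of the table in step 2.

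The Auer rod half is also weaker. CRh needs a marrow result, and marrow samples are evaluated for morphology (Protocol 10.7), so the specimen has been examined. The documents do not list baseline Auer rods as collected, so any condition must key on an earlier positive report.

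It could be added that some protocol sections describe CRh briefly, naming only blasts and counts. They still call it a CR with partial count recovery, and the SAP keeps both features as conditions of the derivation.

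Four stronger readings are tempting and not supported:

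- *Such a CRh has no evidence of clearance at all.* Blasts <5% and both counts must still be documented. The gap is confined to the two features.
- *The rule overrides investigators' non-CR calls.* CRh is designed to be derived from non-CR assessments and relabels nothing as CR.
- *One to nine subjects are affected* (4 × 25% = 1 to 20 × 45% = 9). This applies the whole CR+CRh rate, of which 20 to 40 points are CR. It would need every exposed subject to be denied CR, CRi and MLFS throughout.
- *The default breaches the protocol's missing-data rule.* Protocol 12.11 says "No imputation will be performed for missing data elements unless specified otherwise"; the SAP line is such a specification.

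Finally, the rule is prespecified and identical in both arms of a double-blind trial, and CR+CRh is tested only after OS, which has 54% stated power. Investigator-based CR+CRi and ORR are reported alongside, and DOCRh and TTCRh are not alpha-controlled. All of this stands. The documents give no mechanism for false CRh in one arm only, so the 3.6% in step 4 shows sensitivity and is not an expected error rate. Blinding does not guarantee balance either, since the default acts only when blasts are <5%, and the plan expects more responses with AG-120 (OR 52% vs 32%).

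**Conclusion.** The concern holds in narrow form. As written, the derivation can give CRh to a subject with documented extramedullary disease or Auer rods and no later negative finding, contrary to the CRh definition. It does so only where blasts and counts qualify and the investigator called neither CR, CRi nor MLFS.

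The effect is probably about 0.2 to 1 subject. That rests on the assumed 2-10% prevalence and on these subjects reaching CRh at the planned 5-point rate. It would be larger if investigators often withheld CR, CRi and MLFS solely because extramedullary disease had not been re-examined; the documents give no sign of that. EFS and the CR rate do not depend on the rule. The point is worth correcting because the endpoint is Sponsor-derived and alpha-controlled, and the correction is easy.

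**What to change.** Amend the two default lines in SAP 7.7.2.3 before unblinding:

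- Assume negative if not reported only where there is no earlier documented positive: baseline extramedullary disease recorded as yes, or any prior positive report of either feature.
- After a documented positive, require a documented negative at or before the assessment. An investigator CRi or MLFS at or before it counts as a documented negative. Otherwise the assessment is not CRh.
- Leave baseline extramedullary status of unknown or not assessed under the default, and add a sensitivity analysis of CR+CRh that counts such subjects as non-CRh.

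The cost is a few lines of SAP wording and one sensitivity analysis. The extramedullary part uses a baseline item already listed in SAP 7.3.2; the Auer rod part needs only earlier positive reports, not a baseline field. The CR+CRh rate may fall by a subject or so.

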7.7.2.4. Objective Response

Objective response rate is defined as the rate of CR, CRi (including CRp), PR, and MLFS.

The best response is calculated using the following hierarchy: 1) CR; 2) CRi (including CRp); 3) PR; and 4) MLFS.

Frequency of subjects with best response of CR, CRi (including CRp), PR or MLFS will be tabulated by treatment arm.

If the primary analysis of EFS, CR, OS and CR+CRh are statistically significant, a CMH test stratified by the randomization stratification factors will be used to compare ORR between the 2 treatment arms at 1-sided 2.5% level of significance. The odds ratio and its associated 95% CI will be presented.

7.7.3. Additional Secondary Efficacy Endpoints

Only disease assessments performed on or before the start date of any further anticancer therapies will be considered in the analyses of these endpoints.

7.7.3.1. Complete Remission and CRi (Including CRp)

The CR+CRi (including CRp) rate is defined as the proportion of subjects who achieved a CR or CRi (including CRp). A CMH test stratified by the randomization stratification factors will be used to compare CR+CRi (including CRp) rate between the 2 treatment arms and the nominal 1-sided p-value will be presented. The odds ratio and its associated 95% CI will be presented as well.

